		At study beginning, all households in the villages will be informed about the study. Prior to performing any trial assessments that are not part of routine medical care for the subject, the Investigator or an appropriate designee (if local regulations permit) will obtain written pre-screening consent from one of the parents or a legal representative of the subject to allow the diagnosis activities and the identification of infected children as described in Section 9.2.

Parents/legal representatives of participating subjects will be provided with plastic containers labelled with unique identification numbers (IDs) at the first day of pre-screening. They will be instructed to collect stool and urine samples of the child, each in one of the two separate containers. Stool and urine samples will be processed on the same day.

Pre-screening diagnosis of *S. mansoni* infection will be done using a single POC-CCA urine cassette test. Subjects who are positive for POC-CCA test will provide:

- One urine sample to assess *S. haematobium* coinfection using the filtration technique. One urine sample will be collected from each subject .10 ml of urine samples will be filtered through a filter mesh which will be then examined under the microscope for *S. haematobium* egg count. *S. haematobium* positive diagnosis is defined as positive egg counts of *S. haematobium* in urine (> 1 egg/10 ml of urine) according to WHO classification: light (<50 eggs/10 ml of urine) and heavy (≥50 eggs/10 ml of urine) infections.
- Two stool samples to assess infection intensity using the Kato-Katz method. Two stool samples will be collected from each subject on different days within a maximum of 5 days, at day -28 to day -1 as baseline and 14-21 days after dosing. Infection intensity (expressed as egg count per gram of stool (epg)) will be calculated for each individual. *S. mansoni* positive diagnosis is defined as positive egg counts of *S. mansoni* in stool (>1 egg/1 occasion) according to the WHO classification: light (1-99 eggs per gram of faeces), moderate (100-399 eggs per gram of faeces) and heavy (≥ 400 eggs per gram of faeces) infections.

26 7.1.1 Screening

Study participants will be selected from communities living in the PPD

Prior to study onset, a list of all children aged 2-6 years (Part 1) and 3-24 months (Part 2) living in the selected areas will be prepared using records obtained from the latest census.

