7.4.3 Clinical Laboratory Assessments

Stool, urine and blood samples will be collected according to the schedule given in Appendix II. The volumes of biological fluids collected at each assessment time point are presented in Appendix III. All samples should be clearly identified. Detailed description of the procedures and methods as well as the safety laboratory parameters (haematology, biochemistry and urinalysis) analysed at screening and at the End of Study visit will be given in a separate laboratory manual.

For screening diagnosis of *S. mansoni* infections urine samples will be subjected to a commercially available POC-CCA cassette test.

For diagnosis of *S. mansoni* infections, stool samples will be analysed by Kato-Katz method. Briefly, three Kato-Katz thick smears (41.7 mg) will be prepared from each stool sample (2 stools samples, 3 Kato-Katz smears per stool, i.e. total of 6 smears per subject) and read under a microscope following the instructions of the Kato-Katz manual from the World Health Organization. Infection levels will be determined as described in Section 7.1.1.

For diagnosis of *S. haematobium* co-infections, urine samples will be analysed by the filtration technique. Briefly, urine samples will be strained through filter paper and examined under the microscope for presence of *Schistosoma* eggs.

The Sponsor should receive a list of laboratory normal ranges before shipment of trial drug. Any change in laboratory normal ranges during the trial should be forwarded to Sponsor.

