## 7 Sample Size/Randomisation

## 7.1 Sample Size

Part 1: this study is exploratory. There is no hypothesis testing.

The sample size is based on the minimum number of subjects to reach a meaningful precision of the primary efficacy endpoint estimate (cure rate) in each arm, considering the stratification factor.

There are limited historical data on the impact of the severity of infection on the observed cure rate. In the recent study by Keiser et al. (unpublished data), the observed cure rate in *S. mansoni* infected children varied between 55% and 60% in moderately infected children and 70% and 85% in light infected children depending on the dose. The table below presents the overall cure rate projections according to different assumptions of true cure rate in mild (low) and moderately infected children.

Overall cure rate (95%CI),	Assump	tions of Cure F	Rate in Light In	fections
(N=50)	70%	75%	80%	85%

	50%	62% (48%, 74%)	65% (52%, 78%)	68% (56%, 80%)	71% (60%, 82%)
Assumptions of	55%	64%	67%	70%	73%
Cure Rate in		(50%, 76%)	(54%, 80%)	(58%, 82%)	(62%, 84%)
Moderate/Heavy	60%	66%	69%	72%	75%
Infections		(52%, 78%)	(56%, 80%)	(60%, 84%)	(64%, 86%)
	65%	68% (54%, 80%)	71% (58%, 82%)	74% (62%, 86%)	77% (66%, 88%)

A minimum-clinical meaningful cure rate is considered as equal to 70%. With 50 evaluable patients enrolled, stratified as 40% moderate/heavy and 60% light, the corresponding 95% CI lower bound of an observed cure rate of 70% would be above ~58%, depending on potential difference between the strata. This sample size would also provide the minimum number of subjects to estimate the cure rate within strata.

Considering the efficacy criteria for the selection of the dose (observed cure rate >70%), through simulations, the table below presents the probability of observing an overall cure rate >= 70% based on different scenarios of true cure rates based on different strata, assuming a stratification of 40% moderate/heavy infections and 60% light infections.

Probability of observ	ring a	Assumptio	ns of Cure I	Rate in Ligh	t Infections
cure rate $\geq 70\%$ , N	=50,	70%	75%	80%	85%
	50%	15%	27%	45%	64%
Assumptions of Cure Rate in	55%	23%	38%	57%	76%
Moderate/Heavy Infections	60%	33%	51%	70%	85%
intections	65%	45%	63%	80%	92%

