## 10.2.1 Subgroup definition and parameterization

Subgroup analyses will be performed on subgroups as defined below.

The final parameterization will be updated and fixed at the Data Review Meeting at the latest and documented in an amendment to this SAP if different from the following definition.

The following subgroups will be defined:

- Age (some age ranges may not be applicable, depending on certain trial adaptations) Part 1:
  - 2 years  $\leq$  age < 4 years
  - 4 years ≤ age ≤ 6 years (Ref) Part 2:
  - 3 months  $\leq$  age < 13 months
  - 13 months  $\leq$  age < 24 months (Ref)
- Gender
  - Male (Ref)
  - Female
- Severity of infection (as assessed at Pre-screening [D-28 to D-1])
  - S. mansoni infection
    - Light infection: 1 99 eggs per gram of faeces (Ref)
    - $\circ$  Moderate/heavy infection:  $\geq 100$  eggs per gram of feaces
- Treatment group
  - Biltricide® 3x20mg/kg t.i.d
  - Biltricide® 40mg/kg single dose (Ref)
  - rac-PZQ ODT 1x40mg/kg single dose
  - rac-PZQ ODT 1x60mg/kg single dose
  - L-PZQ ODT 1x30mg/kg single dose
  - L-PZQ ODT 1x45mg/kg single dose
  - L-PZQ ODT 1x60mg/kg single dose
- Trial center/country
  - PPD
  - PPD

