### Clinical cure rate by subgroup:

Again, analyses will be based on responders, which will be defined as was done in section 16.1.1 of this SAP. If the End of Study Kato-Katz egg count is missing, it will be imputed using the LOCF approach. Subgroup analyses of Part 1 and Part 2 of the study will be performed separately, by the following subgroups:

- Age category
- Gender
- Severity of infection
- Trial site (if applicable, i.e. more than one site)

Descriptive statistics of cure rates for each subgroup, individually and all in combination (four-way), will be estimated for each cohort using PROC FREQ.

Subgroup analysis will be performed utilising logistic regression to model clinical cure, i.e. *response* on gender, age category, severity of infection, day of assessment (e.g., Day 14-21), dose, formulation (ODT or not) and active pharmaceutical ingredient (L-PZQ or not [i.e. rac-PZQ]). The analysis will be repeated and presented separately for planned dose (mg/kg) *vs.* actual dose with respect to body weight (mg/kg) and actual dose in mg. Definitions and reference levels of subgroups are described in section 10.2.1 of this SAP. The PROC LOGISTIC procedure in SAS will be used with appropriate DESCENDING (to model on *response*=1) and PARAM=REF

(dummy coding for parameter estimates) statements to determine odds ratio point estimates and corresponding 95% Wald CIs.

To compliment PROC LOGISTIC results, the diagnostic plots using Pearson residuals will be produced [PLOTS(ONLY LABEL)=(INFLUENCE)].

Cure rate, in terms of proportion of responders, will be summarised by cohort (and by infection severity), and listed by cohort and subject. Estimates of cure rate will be presented graphically in the form of a forest plots presenting means and 95% CIs, by subgroup and cohort. For logistic regression results, odds ratio point estimates of model parameters and corresponding 95% CIs will be presented for each parameter, by cohort. Dose-response curves will be presented for the different active pharmaceutical ingredients (rac-PZQ/L-PZQ), separated by severity of infection, as well as pooled (all infections). Dose response curves will be generated for planned dose (in mg/kg), actual dose with respect to weight (in mg/kg) and actual dose in mg. These summary tables will be followed by the respective diagnostic plots.

Results will be presented for each analysis set.

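### The supportive dose-response model for Kato-Katz cure uses baseline egg count only as light versus moderate/heavy; adding log epg would be a small, nearly free gain in precision

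*Protocol*

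**What the plan says.** Protocol 7.1.1 (Pre-screening), on the baseline stool samples: "Infection intensity (expressed as egg count per gram of stool (epg)) will be calculated for each individual". Protocol 7.4.3 gives the amount of stool behind that figure: two stools, "3 Kato-Katz smears per stool, i.e. total of 6 smears per subject", each smear 41.7 mg.

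SAP 16.1.2 models Kato-Katz cure by logistic regression on "gender, age category, severity of infection, day of assessment (e.g., Day 14-21), dose, formulation (ODT or not) and active pharmaceutical ingredient" (L-PZQ or not). It adds that "Definitions and reference levels of subgroups are described in section 10.2.1 of this SAP". Section 10.2.1 gives severity two levels. The reference level is light infection, with an upper limit of "99 eggs per gram of faeces (Ref"). Everything from 100 epg upward forms the second level, so the moderate and heavy classes that the protocol lists separately are merged. No continuous baseline count enters the model.

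The same split is the randomisation stratum (60% light, 40% moderate/heavy; Protocol 8.2, SAP 7.2). C1 to C6 are filled to 40 per arm. If C7 is opened, allocation then runs 1:1:1:1:1:1:3 up to 60 per arm.

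SAP 16.1.2 is headed as supportive. The primary analysis (SAP 16.1.1) is the unadjusted cure rate per cohort with a Clopper-Pearson interval and no hypothesis test.

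**The concern.** The endpoint is zero eggs in about a quarter of a gram of stool, so the chance of cure plausibly falls steadily as baseline burden rises. A two-level term keeps only the part of that gradient that crosses 100 epg: a child at 8 epg counts the same as one at 96, and one at 100 the same as one at 2000.

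The plan itself treats burden as prognostic. It is the only stratification factor, and the only baseline factor for which SAP 7.1 quotes cure rates by level: in a recent study they "varied between 55% and 60% in moderately infected children and 70% and 85% in light infected children depending on the dose".

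The model matters because exploring dose-response is a secondary objective (Protocol 4.2) and, with PK sampling abandoned, dose-response replaces exposure-response (Protocol 5.2). The other dose-on-cure analyses, the per-cohort rates and the trend tests of SAP 16.3.2, are unadjusted. At stake are the precision of the adjusted dose odds ratios and their protection against differences in burden within a class.

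**Working it through.** **Resolution of the count.** 6 x 41.7 mg = 250.2 mg, and 1000/250.2 = 4.0 epg per egg. This agrees with the multiplier of four in SAP 16.2.2.

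**The plan's own figure.** With 30 light children at 85% and 20 moderate/heavy at 60%, P(at least 35 of 50 cured) from the two binomials is 84.7%, against the stated 85%. All 16 cells of that table reproduce within 1 point. None depends on the model in SAP 16.1.2.

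**Assumptions not in the documents.** Log epg is normal with 60% below 100 epg. The logit of cure is linear in log epg, calibrated to given light and moderate/heavy cure rates. The SD of ln(epg) is 1.2 or 1.6, with a floor of 4 epg, for the power runs. Counting error is ignored.

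**1. Information kept by the split.** The cut is at z = 0.253, where the normal density is 0.386. Share of log-epg variance kept = 0.386^2/(0.6 x 0.4) = 0.62, so 38% is lost. Three levels (light, moderate, heavy) would keep 68-71%.

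**2. Imbalance left within classes** (85%/60%, overall 75%, two arms of 60).
- Variance of cure probability due to burden: 0.0226 (numerical integration).
- Between classes: 0.6 x (0.85-0.75)^2 + 0.4 x (0.60-0.75)^2 = 0.0150. Within classes: 0.0076.
- SD in the arm difference: sqrt(2 x 0.0076/60) = 1.6 points.
- SE of the difference after stratification: sqrt(2 x (0.1875-0.0150)/60) = 7.58 points. With burden fully adjusted: sqrt(2 x (0.1875-0.0226)/60) = 7.41 points, about 2% shorter.

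**3. Power for the L-PZQ dose term** (3 x 60 children, 0.5 log-odds per dose step, two-sided 5%; 4,000 runs per scenario in the first two rows, 8,000 in the last two). The rows span the cure rates quoted in SAP 7.1.

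| Light / mod-heavy cure | Within-class SD of arm difference | Class only to class + ln(epg), SD 1.2 | Same, SD 1.6 |
|---|---|---|---|
| 70% / 60% | 0.65-0.67 points | 71.3% to 71.6% | 70.1% to 71.0% |
| 75% / 60% | 0.96-0.98 | 68.8% to 69.2% | 68.2% to 68.7% |
| 80% / 57.5% | about 1.4 | 63.8% to 65.1% | 63.3% to 64.5% |
| 85% / 55% | up to 1.85 | 56.7% to 59.1% | 57.1% to 59.3% |

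The paired difference has a standard error of 0.3 points at 8,000 runs, so the smallest gains are close to simulation error.

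**4. Attenuation and type I error** (two concurrent arms of 60, true dose odds ratio 2.5, 3,000 runs). Mean log odds ratio, class versus continuous log epg:
- 85%/60%: 0.953 versus 0.998, a shortfall of 4.5%.
- 85%/50%, the widest gap in the plan's table: 0.902 versus 0.980, or 8%.
- 70%/65%, the narrowest: 0.945 versus 0.947.

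Both codings carry small-sample bias, so they are compared with each other rather than with ln 2.5 = 0.916. With no dose effect, mean log odds ratios lie within about 0.015 of zero and rejection is 3.9-4.6% for both.

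**5. C7.** 40/60 = two-thirds of C5 and C6 are randomised before any C7 child. The documents give no drift figure. As an illustration, assume burden rises 1.5- to 2-fold after C7 opens (2,000 runs per scenario). The class-only model then gives a mean of 0.43-0.47 log-odds per step (true 0.50) with power 47-62%; adding ln(epg) gives 0.51-0.53 with power 60-68%. A fall in burden would shift the class-only estimate the other way.

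**The case against.** The other side has a good case, and most of it stands.

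- The model is supportive and the trial exploratory. The primary cure rates and the efficacy criterion (observed cure rate above 70%) use no covariate, so power for a dose term is not a design quantity. This stands, and it limits the weight of the point.
- Randomisation and model already share the light versus moderate/heavy split. With concurrent arms, what remains is ordinary sampling error inside a standard error of roughly 8 points. This stands for C1 to C6. It does not cover C7, because stratification does not guarantee equal burden within a class between children enrolled at different times.
- The attenuation is non-collapsibility: the odds ratio given class and the odds ratio given class plus epg are different conditional quantities. This is correct, so the attenuation should not be called bias.
- Class and log epg are strongly correlated (r = sqrt(0.62) = 0.79), so the severity odds ratio becomes hard to read when both are in the model, and linearity of the logit is untested. Both are real but manageable costs.
- Baseline counts are used in full in the egg reduction rates (SAP 16.2.2). True, but that is a different endpoint and does not adjust the cure model.

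A reader might infer that the plan discards most of the information in its strongest baseline predictor. The documents do not rank predictors, and SAP 7.1 calls the historical data on severity and cure limited. Under the stated assumptions the split keeps more than half of the information.

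**Conclusion.** The point holds as a minor precision improvement. An epg exists for every child, and the only covariate-adjusted dose-response model for Kato-Katz cure uses it at two levels, leaving within-class differences unadjusted.

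With concurrent arms the effect is small: a power gain of about 0.3 to 2.5 points and an odds-ratio attenuation of up to about 8%, reached only at the widest gap in the plan's table. These figures rest on log-normal epg, a linear logit and an assumed dose effect. Counting error would lower them; heavier tails or a steep gradient within the moderate/heavy class would raise them. The drift result for C7 shows a vulnerability, not an expected effect.

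A reader might also infer that the dose comparison is biased or that dose selection is at risk. The documents do not support either: there is no type I error inflation with concurrent arms, and neither the primary per-cohort rates nor the 70% criterion passes through this model.

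**What to change.** In SAP 16.1.2, prespecify log10 of each child's baseline epg (from the six pre-treatment smears) as a continuous covariate in the Kato-Katz cure model. Keep the light versus moderate/heavy term, since it is the randomisation stratum, and report the dose odds ratios from this model. Take the severity odds ratio from the model without log epg, because the two terms are correlated. Keep the descriptive tables and curves by class. Name a spline in log epg as the check on linearity.

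The cost is a few lines of SAP text, one model term and one sensitivity fit. No new data are needed, and the sample size and primary analysis stay as they are. The term adjusts only for drift in egg burden, not for other changes over calendar time.

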7.1.3 Treatment period

In case several assessments are planned at the same time point, the PK samples will be taken at the predefined time point. Vital signs will be recorded before PK samples.

Pre-dose assessments

Subjects will undergo physical examination, vital signs assessment and re-check of eligibility criteria. If assessments have been done on the same day they do not need to be repeated. PK sample will be taken within maximum 1 hour prior to dosing.

Post-dose assessments

PK samples will be taken according to the sampling scheme (see Section 0). The allowed deviation from the pre-specified assessment will be ± 10% (in minutes) of the scheduled time point. In case several assessments are planned at the same time point, the PK samples will be taken at the pre-defined time point.

In cohort C1–Vital signs will be recorded 8 hours after first dosing, before PK samples are taken. Physical examination will be performed 8 and 24 hours (± 10% in hours) after first dosing, before PK samples are taken. PK sampling after the first dose should be taken before the second dose is administered.

In cohorts C2 C9, vital signs will be recorded 8 hours after dosing, before PK samples are taken. Physical examination will be performed 8 and 24 hours (± 10% in hours) after dosing, before PK samples are taken.

Clinical safety laboratory evaluations (i.e. hematology, biochemistry and urinalysis) and urine collection for POC-CCA test will be performed 24 hours (± 10% in hours) after dosing. All biological assessments will be performed in fasting condition, if possible.

Clinical safety laboratory evaluations (i.e. hematology, biochemistry and urinalysis) and urine collection for POC-CCA test will be performed 24 hours (\pm 10% in hours) after dosing. All biological assessments will be performed in fasting condition, if possible.

In case the participant, due to logistical or social reasons will have to spend an additional night in the hospital, the end of confinement will be documented after the specified 18/24 Hours and the additional night will not be considered as part of confinement. As such, it will not qualify as SAE, as described in section 7.4.1.1.

28 7.4.1.2 Safety Reporting to Health Authorities, Independent Ethics Committees/Institutional Review Boards and Investigators

At each trial visit, the subject and the parents/representatives will be queried on changes in his or her condition..

At each trial visit, From screening visit to end of study, the subject and the parents/representatives will be queried on changes in his or her condition.

29 7.4.1.3 Definition of the Adverse Event Reporting Period

The AE reporting period for safety surveillance begins when the subject is initially included in the trial (date of first signature of informed consent) and continues through the trial's post treatment follow-up period until the End of Trial Visit.

The AE reporting period for safety surveillance begins when the subject is initially included in the trial at screening visit, (date of signature of informed screening consent) and continues through the trial's post treatment follow-up period until the End of Trial Visit.

30 7.5. Pharmacokynetics

[...]

Not applicable

31 8.4 Analysis sets

[...]

PK analysis sets:

There will be two analysis sets, one for non-compartmental PK analysis (NCA) and one for Population PK. The NCA Analysis Set will consist of all subjects who receive at least one dose of any formulation of PZQ, have been allocated to rich PK sampling, have no protocol deviations affecting PK and provide at least three measurable post-dose concentrations. The Population PK Analysis Set will consist of all subjects who receive at least one dose of any formulation of PZQ, have no protocol deviations affecting PK and provide at least one measurable post-dose concentration.

Subjects will be analyzed according to the actual treatment they received. All concentrations measured will be included in the descriptive statistics for concentration data.

[...]

PK analysis sets:

There will be two analysis sets, one for non-compartmental PK analysis (NCA) and one for Population PK. The NCA Analysis Set will consist of all subjects who receive at least one dose of any formulation of PZQ, have been allocated to rich PK sampling, have no protocol deviations affecting PK and provide at least three measurable post dose concentrations. The Population PK Analysis Set will consist of all subjects who receive at least one dose of any formulation of PZQ, have no protocol deviations affecting PK and provide at least one measurable post-dose concentration.

Subjects will be analyzed according to the actual treatment they received. All concentrations measured will be included in the descriptive statistics for concentration data.

32 8.5 Analysis sets

All efficacy, safety and pharmacokinetic endpoints All efficacy and safety and pharmacokinetic endpoints will be analysed descriptively. Graphs will be analysed descriptively. Graphs will be produced as appropriate. Point estimation and 95% will be produced as appropriate. Point estimation confidence interval (CI) will be calculated for and 95% confidence interval (CI) will be calculated primary and key secondary endpoints for each for primary and key secondary endpoints for each treatment arm. treatment arm. 33 8.5.1 General considerations Pharmacokinetic calculations Pharmacokinetic calculations See Section 7.5.2 Not applicable. 34 8.6 Interim and Additional Planned Analyses [...] [...] At the end of Part 1, the final analysis will be At the end of Part 1, the final analysis will be conducted on data as clean as possible. The Safety conducted on data as clean as possible. The Safety Monitoring Committee will assess the data (safety, Monitoring Committee will assess the data (safety efficacy and PK) in order to recommend an optimal and efficacy) in order to recommend an optimal ODT dose (L-PZQ or rac-PZQ) for Part 2. This ODT dose (L-PZQ or rac-PZQ) for Part 2. This optimal ODT dose (L-PZQ or rac-PZQ) will be optimal ODT dose (L-PZQ or rac-PZQ) will be corrected by using allometric scaling of the PK data corrected by using allometric scaling of the PK data available from Part 1 as well as a maturation factor available from Part 1 as well as a maturation factor (to compensate for the immature metabolic system (to compensate for the immature metabolic system in infants), in order to identify the appropriate in infants), in order to identify the appropriate dose(s) to treat cohorts 8 and 9. dose(s) to treat cohorts 8 and 9. 35 9.2 Subject Information and Informed Consent [...] [...] A subject information sheet must be prepared in the A subject information sheet must be prepared in the local language PPD local language, PPD) in accordance with ICH in accordance with ICH GCP and will be provided by the Sponsor for the GCP and will be provided by the Sponsor for the purpose of obtaining informed consent/assent. purpose of obtaining informed consent/assent. 9.6 Independent Ethics Committee or Institutional Review Board Prior to commencement of the trial at a given site, Prior to commencement of the trial at a given site, this clinical trial protocol will be submitted together this clinical trial protocol will be submitted together with its associated documents (e.g., informed with its associated documents (e.g., informed consent form, documents of subjects data collection, consent form, documents of subjects data collection, certificate of insurance, etc.) to the responsible certificate of insurance, etc.) to the responsible IECs/IRBs (PPD IECs/IRBs PPD) for their favourable opinion or) for their favourable opinion approval, which will be filed in the Investigator Site or approval, which will be filed in the Investigator Site File. A copy will be filed in the Trial Master File. File at PPD Contact details of the PPD Contact details of the PPD are as are as follows: follows: PPD PPD PPD PPD

	Tel: PPD E-mail: PPD E-mail: PPD			
37	9.7 Health Authorities			
	The clinical trial protocol and any applicable documentation (e.g., Investigational Medicinal Product Dossier, Subject Information and Informed Consent Form) will be submitted or notified to the Ivory Coast and Kenyan Health Authorities in accordance with their national regulations and requirements.	The clinical trial protocol and any applicable documentation (e.g., Investigational Medicinal Product Dossier, Subject Information and Informed Consent Form) will be submitted or notified to the Ivory Coast and Kenyan Health Health Authorities in accordance with its national regulations and requirements.		
38	10.4 Monitoring, Quality Assurance and Inspection	by Health Authorities		
	This trial will be monitored in accordance with the ICH GCP guidelines and any other applicable regulations. The site Monitor will perform visits to the trial site at regular intervals according to the monitoring plan.	This trial will be monitored in accordance with the ICH GCP guidelines and any other applicable regulations. The site Monitor will perform off-site and on-site visits at regular intervals according to the monitoring plan.		
39		Signature Page – Sponsor Medical Responsible		
		Function/Title: Medical Responsible Institution: Merck KGaA Address: [name] [name] Telephone number: PPD Fax number: PPD E-mail address: PPD		
40	Signature Page – Coordinating Investigator			
41	Name, academic degree: PPD Function/Title: Coordinating Investigator Institution: PPD Telephone number: PPD E-mail address: PPD	Name, academic degree: PPD Function/Title: Coordinating Investigator Institution: PPD — — — — — — — — — — — — — — — — — —		
41	Appendix II:Table of study procedures and assessn PK sampling			
	rk sampling	PK sampling		

42	Appendix II: Table of study procedures and assessments - Cohort C2-C7					
	PK sampling	PK sampling				
43	Appendix II: Table of study procedures and assessments - Cohort C8-C9					
	 ICF signature at pre-screening (D-28 to D-1) Malaria rapid diagnostic test at pre-screening (D-28 to D-1) or at screening if not done at pre-screening PK sampling 	 Pre-screening consent at D-28 to D-1 ICF signature at pre-screening (D-7 to D1) Malaria rapid diagnostic test at screening (D-7 to D1) PK sampling 				
44	Appendix III: Volume of biological fluid collected a	at each assessment time point (Cohorts C1-C7)				
